minutes each is comprised of the CSNAT approach [Sessions 1 & 2] and Respecting Choices [Session 3]. Investigators will test the initial efficacy of FACE-Rare on measurable outcomes at baseline and 3-months post-intervention. See **D5** for description of intervention. See **Power Analysis** for rational for 30 dyads. D.2. Study Population. Nearly half of all pediatric inpatients in tertiary hospitals suffer from life-threatening diseases, and of these 82% have rare diseases. 139 A profile of children in the last year of life revealed that 56% had multiple complex chronic conditions. 139 For this reason investigators will include children with multiple-morbidities and include the large proportion of children with rare diseases treated in tertiary hospitals who are unable to communicate because of age, untreatable communication disorder, or intellectual disability. If multiple family caregivers participate, data will only be used for the primary caregiver, as determined by the couple. However, data will be collected from all participants for secondary analysis. Child inclusion criteria are (1) ≥1.0 years and <18.0 years at enrollment; (2) unable to participate in end-of-life care decision-making; (3) have a rare disease as operationally defined (See Human Subjects); (4) not under a Do Not Resuscitate Order or Allow a Natural Death Order; and (5) not in the Intensive Care Unit. Family caregiver inclusion criteria are: (1) > 18.0 years at enrollment; (2) legal guardian of child and child's caregiver; (3) can speak and understand English; (4) not known to be developmentally delayed; and (5) not actively homicidal, suicidal or psychotic at the time of enrollment. Investigators will collect data on reasons for declining. D.2.a. Study Site. Children's National has an internationally recognized clinical genetics program, which records over 8,000 patient visits a year. The Children's National Rare Disease Institute is the first of its kind, focused exclusively on advancing the care of children with rare diseases. Eligible families will be enrolled from Children's National (N=32 dyads). Based on previous research, 5-9,56 investigators estimate 50% of families approached will agree to enroll, and 1% will be ineligible at secondary screening. So to achieve our randomization goal of 30 family/child dyads investigators will need to approach 32 families, which is realistic. **D.3. Recruitment and Retention Plan.** Recruitment will use principles of inclusiveness. Investigators recognize that disease progression may impact enrollment and will take steps to accommodate caregivers. See Human Subjects and. Investigators will recruit during clinic visits, but not on day of diagnosis. The site's

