
team is experienced and will use methods described by rare disease researchers.⁴ Recruitment Procedures: Investigators will use a two-step recruitment procedure that ensures involvement of the primary provider or medical care team and reduces the potential burden to families. To minimize gatekeeper bias, prior to study initiation, investigators will conduct educational forums to discuss the study and address the legitimate reasons for providers to refuse approach. First, the study team will identify potential patients through review of future appointments. Second, the health care provider will confirm eligibility criteria, e.g. patient does have a rare diagnosis and the condition is not a result of prematurity, such as in pulmonary hypertension. The health care provider will let the study team know if there is a reason not to approach the family. Third, a trained member of the study team will approach the family by email and/or telephone, and/or text, as long as COVID-19 prevents face-to-face approaches. The selection, roles, responsibilities, and preparation of families are detailed in the 3-day Protocol Training. "Because of COVID-19 and the difficulty with face-to-face recruitment posed by the epidemic, we are requesting to ADD to our recruitment strategy a modified form of Snowball Recruitment. 1. Potential participants will be contacted by previous participants (from the beta testing phase of our study in 2019) who are currently members of our Community Advisory Board (CAB). We are asking them to tell other people about the study. The CAB member will use the IRB approved flyer to describe the study to other people (family caregivers of children with rare diseases, whose child receives care at Children's National, and whose child is between the ages of 1 up to age 18) who may be eligible. If interested these people will contact the researcher directly using the researchers' contact information on the IRB approved Flyer. This approach will protect patient privacy. 2. We will not be doing "cold calling." 3. CAB members will not be receiving any compensation for providing referrals or be offered incentives to provide referrals. 4. Current participants will not be required to refer others or incur any penalty for not referring other participants. 5. The CAB member do not have power over the potential participants, such as an employeremployee relationship, but may be members of various advocacy groups that support family caregivers." Consent and Enrollment: Family caregivers will undergo written informed consent using IRBapproved documents prior to participation in any study procedures or data collection. Investigators have IRB approval for a waiver of assent for the children, as one eligibility criterion is "unable to participate in healthcare decision making." Randomization and Blindness: Randomization will be triggered by computer following completion of the baseline assessment in the already established REDCap database. Employing an intent-totreat paradigm, dyads will be randomly assigned to FACE-Rare vs. TAU at a ratio of 1:1. The FACE-Rare

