
PROTECTION OF HUMAN SUBJECTS FROM RESEARCH RISK

1. Risks to Human Subjects

a. Human Subjects Involvement, Characteristics and Design

We will be studying family caregivers/legal guardians of children ages ≥1 to <18 years with rare diseases who are unable to participate in health care decision making; and retrieving protected health information on the children from the electronic health record (EHR). No data will be collected directly from the children, but PHI will be collected from the EHR.

Children's National Health System serves approximately 2,189 children who meet eligibility criteria, including children with Leukodystrophies; Intestinal Failure/Short Bowel Syndrome/Liver failure; Pediatric Cardiomyopathies; Organic Acidemias; Renal Failure in need of Renal Replacement Therapy (Dialysis and kidney transplants); Rare clotting disorders; Hemophilia A inhibitor, Severe. Our site has a history of successful research.

We will recruit for approximately twelve months until we enroll *30* family caregiver/child dyads who after completion of the baseline questionnaires will be randomized at a ratio of 1:1 into either the 3-session FACE-Rare Intervention Group (n=15 dyads) or Treatment as Usual Control Group (n = 15 dyads) with the goal of obtaining data from conservatively 21 dyads at 3 month post-intervention for statistical analysis. We have not had differential attrition in our earlier studies, as discussed in

Research Strategy. We estimate that approximately 43% of the sample will be African-American. To achieve our enrollment goal of 30 families, we estimate based on our previous studies that we will need to approach 62 families, which should be easily accomplished with the potentially available study population. Post-intervention questionnaires to asses study outcomes will be administered at 3-months post-intervention.

The current R21 proposal has received approval from Children's National's IRB, the IRB. The participant eligibility criteria have been developed with careful consideration to ensure the safety of the study participants.

Participant Eligibility Criteria

Child Inclusion Criteria:

- Diagnosed with a rare disease;
- Ages ≥1 year <18 years; no infants under the age of 1 year are included;*
- Not in foster care;
- Unable to participate in health care decision making, e.g. due to developmental delay (IQ <70), neuromuscular disorder with no communication device, under age 7;
- Waiver of assent from the legal guardian;

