Recruitment Procedures: We will utilize a three-step recruitment procedure that ensures involvement of the health care provider or medical care team to reduce the potential burden to families. To minimize gatekeeper bias, prior to study initiation, we will conduct primary care provider and healthcare team educational forums to discuss the study and address the legitimate reasons for providers to refuse approach. The study team at each site will identify potential patients through review of future appointments. First, the study team will identify potential patients through review of future appointments. Second, the health care provider will confirm eligibility criteria, e.g. patient does have a rare diagnosis and the condition is not a result of prematurity, such as in pulmonary hypertension. The health care provider will let the study team know if there is a reason not to approach the family. Third, a trained member of the study team will approach the family by email and/or telephone, and/or text, as long as COVID-19 prevents face-to-face approaches. Eligible families will be approached until 30 eligible dyads are enrolled. The selection, roles, responsibilities, and preparation of families are detailed in the 3-day Facilitator Training outlined. [name] and colleagues are currently collaborating on a study that uses a similar procedure and have found it to be successful, i.e. not burdensome to the family caregiver.

Children's National has a history of success in recruiting children and families for participation in research studies. Currently, Children's National is running two clinical trials. We are especially sensitive to the distress of families of children living with rare diseases and to recruitment during the end-of-life. For this reason we will maintain the involvement of a Community Advisory Board of Families of Children with Rare Diseases and NORD throughout the study. See **Overall Structure of Study Team**. We will generate a list of potentially eligible participants and follow the procedures described in **Recruitment and Enrollment Plan**.

Attrition: See **Approach** for data on attrition. In the PI's judgment, Children's National has such low attrition because patients form strong attachment bonds with the clinical and research staff, a "positive institutional transference" ([name]. personal communication, former director of the Family Research Center at George Washington University).

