All participants will receive a secondary screening. We will ask for a waiver of consent for those who decline to participate so we can gather demographic data on decliners. This will enable us to determine if there is a significant difference between acceptors and decliners. These sheets will be assigned a unique identifier number. Consent at this time will be for data collection for the child from the EHR through medical chart abstraction and from study questionnaires from the legal guardian/family caregiver at baseline assessment and 3-month post-intervention.

Consent will also include a release to give the child's primary HCP a copy of the advance care plan. A copy of the advance care plan and a summary statement of the respecting choices conversations about goals of care in a HIPPA compliant email will be given to the primary health care providers for their records. No other data will be shared with the HCP.

Assent will be waived for all child participants, as an entry criterion is being unable to participate in decision making. Legal guardian/family caregiver consent to participate (for both their child and themselves). Participants will be assessed to determine readiness to participate, to identify obstacles

to participation, and to enhance motivation. They will be given ample time to answer questions. This process is expected to take 20-30 minutes.

The consent and assent waiver forms describe the nature of the screening phase, right to refuse to answer any questions and to withdraw from the screening process at any time without penalty, methods in place to protect confidentiality, and limits of confidentiality (e.g., suicidal/homicidal intent). The consent form describes the nature of participation, rights of refusal to answer any question and to withdraw at any time without penalty, methods in place to protect confidentiality, and limits of confidentiality (e.g., child abuse/neglect, suicidal/homicidal intent).

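### The acceptor-decliner comparison mixes recruitment route with willingness and is too small for a non-significant result to indicate representativeness

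*Combined protocol and SAP*

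**What the plan says.** In the protocol's human subjects part, section 2 (Adequacy of Protection Against Risks), under informed consent and waiver of assent, the plan states: "We will ask for a waiver of consent for those who decline to participate so we can gather demographic data on decliners". It continues: "This will enable us to determine if there is a significant difference between acceptors and decliners". No test, precision target or rule for reading a null result accompanies this, and the Analytic Plan (D.9) does not mention the comparison.

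Three other places determine who falls into each group:

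- **Snowball route (D.3, Recruitment Procedures).** Community Advisory Board members pass the study flyer to other caregivers. "If interested these people will contact the researcher directly".
- **Provider veto (D.3).** "The health care provider will let the study team know if there is a reason not to approach the family".
- **Numbers.** Under Recruitment Procedures in the human subjects part: "Eligible families will be approached until 30 eligible dyads are enrolled". Section 1.a of that part says "we will need to approach 62 families, which should be easily accomplished with the potentially available study population", whereas D.2.a says "investigators will need to approach 32 families, which is realistic".

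The plan also collects reasons for declining (D.2) and logs refusals so that they can be inspected for patterns (human subjects part, informed consent).

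**The concern.** An acceptor-decliner comparison is informative when both groups come from the same set of invited families and every invitation ends in a recorded yes or no. The clinic route roughly meets that condition. The snowball route does not, because a family that hears of the study and is not interested leaves no trace, while one that enrolls joins the acceptors. Nothing in the plan marks which route a family came by. Families withheld by the provider are in neither group.

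The criterion is also statistical significance, applied to two groups of about 30. Substantial selection could easily go undetected.

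What is at stake is how far the 30 families can be said to represent those eligible. The plan cares about this: equity for African-American caregivers is part of its rationale, and the pilot is meant to inform a larger trial.

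**Working it through.** **Inputs from the protocol**
- Acceptors: 30 dyads.
- Families approached: 62 (section 1.a, human subjects) or 32 (D.2.a).
- Agreement 50%; ineligible at secondary screening 1% (D.2.a).
- Reference trait: 43% of the sample expected to be African-American (section 1.a).

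**Assumptions, because none is stated for this check:** two-sided Fisher's exact test at 5% (borrowed from D.9), 80% power, and independent groups.

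**1. Which count of families approached is coherent?** Families needed = 30 / (0.50 × 0.99) = 60.6, or 61. This agrees with 62 to within one family. The other figure does not reproduce: 32 × 0.50 × 0.99 = 15.8 dyads. I use 62, which is also the count kinder to the plan. It leaves 62 − 30 = 32 not enrolled, about 31 of them decliners at 50% agreement.

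**2. Power in the best case (30 v 32, 43% of acceptors with the trait).** Exact enumeration over both binomials:

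| True gap | Power, decliners higher | Power, decliners lower |
|---|---|---|
| 10 points | 11% | 9% |
| 20 points | 30% | 32% |
| 30 points | 61% | 73% |

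A power of 80% needs about 36 points (decliners higher) or 32 points (decliners lower). The 95% half-width of the difference is 1.96 × √[0.43 × 0.57 × (1/30 + 1/32)] = 0.247, about 25 points. For reference rates of 30-70% and other common tests, the detectable gap runs from roughly 26 to 38 points.

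**3. Why this is a best case.** Having 32 decliners requires all 62 families to be approached directly, so almost no enrollee comes by snowball. If *s* of the 30 do, and half of directly approached families agree, recorded decliners number about 30 − *s*. With *s* = 10 the pooled comparison is 30 v 20: power for a 20-point gap is 26%, and 80% power needs about 35-40 points. If only 32 families were approached, about 2 would be decliners, and no gap from 43% reaches 80% power.

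**4. What pooling the routes can do.** The protocol gives no snowball yield or trait rates, so these values are purely illustrative. Suppose directly approached acceptors have a trait at 30% and decliners at 56%, a true gap of 26 points.

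| Snowball enrollees | Trait rate in them | Pooled acceptors | Apparent gap |
|---|---|---|---|
| 10 | 80% | (20 × 0.30 + 10 × 0.80)/30 = 47% | 9 points |
| 5 | 80% | (25 × 0.30 + 5 × 0.80)/30 = 38% | 18 points |
| 10 | 40% | (20 × 0.30 + 10 × 0.40)/30 = 33% | 23 points |
| 10 | 10% | (20 × 0.30 + 10 × 0.10)/30 = 23% | 33 points |

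The distortion can be small or large, and can shrink or widen the gap. Sections 2 and 4 cannot both apply at full strength: the power figures assume almost no snowball enrollees, while these rows assume 5 or 10.

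**The case against.** The strongest reply is that this is one sentence in a human subjects section. It is not an aim, a hypothesis or part of D.9, and the plan already concedes that power is limited in so small a sample. Enrollment precedes randomization, so nothing here biases the comparison of arms. All of that stands, and it sets the priority.

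A reader might go further than the documents allow in four ways:

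- **That this is the plan's only check on selection.** It is not. Reasons for declining are collected and refusals are logged and reviewed, and provider forums aim to limit gatekeeping. However, neither record separates routes or captures snowball contacts who never call.
- **That the comparison can show nothing.** Families who decline after a direct approach are recorded, and so are snowball callers who then refuse. A very large gap could still be seen.
- **That the snowball route is known to bias the result.** The protocol presents it only as an addition because of COVID-19 and gives no expected yield. It may have supplied very few families.
- **That the sponsor will read a null result as representativeness, or carry an inflated acceptance rate into the larger trial.** Neither is written. The stated input to that trial is an effect size.

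There is also a fair objection to the remedy: restricting the comparison to directly approached families makes an imprecise comparison less precise.

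**Conclusion.** The concern holds as a limitation of a peripheral check. As planned, the comparison can pool acceptors from two routes with decliners drawn mainly from one, and nothing recorded would let an analyst separate them. The size and direction of the effect are unknown.

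Separately, a significance criterion is uninformative at this sample size. With 30 v 32, a real 20-point gap from 43% would be missed about two times in three, and 80% power needs about 32-36 points. Those figures rest on the 62-family count, an assumed two-sided 5% Fisher test, an assumed 80% power target, and almost no snowball enrollment. Fewer decliners would make the test weaker. A non-significant result would therefore not be evidence that the enrolled families are representative.

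The documents do not support a stronger conclusion, such as that enrollment is in fact unrepresentative or that the trial's efficacy results are compromised. Priority is low.

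**What to change.** - Add a recruitment-route field in REDCap (approached directly by the team, or self-referred after snowball contact).
- Make the main acceptor-decliner comparison, and any acceptance rate that is reported, among families the team approached directly.
- Show snowball enrollees as a separate column, and give the count of families withheld by the provider.
- Report differences with 95% confidence intervals in place of a significance verdict, and state that non-significance will not be taken as representativeness.
- Reconcile the 62 and 32 families to be approached.

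The administrative cost is one database field and a few sentences. The statistical cost is precision. If 10 or 15 enrollees come by snowball (assumed, with 50% agreement), the direct-approach comparison is 20 v 20 or 15 v 15. The half-widths at 43% are then 1.96 × √[0.43 × 0.57 × (2/20)] = 0.307 and 1.96 × √[0.43 × 0.57 × (2/15)] = 0.354, about 31 and 35 points against 25 in the best case. The pooled result can be shown alongside, labelled as mixing routes.
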